- Congenital anomaly/birth defect.
- Other medically significant events that, based upon appropriate medical judgment, may jeopardize the subject and may require medical or surgical intervention to prevent one of the outcomes listed above, eg, allergic bronchospasm requiring intensive treatment in an emergency room or home, blood dyscrasias or convulsions that do not result in hospitalization, or the development of drug dependency or drug abuse.

Nonserious AEs are all AEs that do not meet the criteria for a “serious” AE.

Adverse Events of Special Interest (AESIs): A noteworthy event for the particular IMP or class of products that a sponsor may wish to monitor carefully. All AESIs are to be reported as immediately reportable events (IREs). No AESIs have been identified for the IMP to be administered during this trial.

Immediately Reportable Event:

- Any SAE.
- Potential serious hepatotoxicity (see [Section 8.6.6](#)).
- Any AE related to occupational exposure (eg, an investigator getting a skin rash after exposure to a medication). Non-subject AEs would not be recorded on the eCRF form but must be recorded on an IRE form to the sponsor.
- Pregnancies are also defined as IREs. Although normal pregnancy is not an AE, pregnancy of a trial subject will mandate trial intervention discontinuation and pregnancy of either a subject or a subject's partner must be reported on an IRE form and the Pregnancy Surveillance Form(s) to the sponsor. This includes pregnancy of the subject or the partner of the subject. Pregnancy will only be documented on the AE eCRF if the pregnancy occurs in a female subject and there is an abnormality or complication (see [Section 10.3](#)).

Clinical Laboratory Test Value Changes: It is the investigator's responsibility to review the results of laboratory tests for each individual subject as they become available. This review will be documented by the investigator's dated signature on the laboratory report. The investigator may repeat the laboratory test or request additional tests to verify the results of the original laboratory tests. If this laboratory value is considered medically relevant (ie, clinically significant) by the investigator (subject is symptomatic, requiring corrective treatment or further evaluation), or if the laboratory value leads to discontinuation, and/or fulfills a seriousness criterion, this is considered an AE.

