9.4.3.2 Clinical Laboratory Data

Descriptive statistics will be used to summarize the change from baseline for laboratory tests by treatment group for each visit. Baseline is defined as the last nonmissing value obtained at a scheduled visit on or before Day -1. If the Day -1 measurement is missing, the baseline value will be the last nonmissing measurement from the screening visit (the previous scheduled visit). The incidence of potentially clinically significant changes and abnormalities in clinical laboratory test parameters will be summarized by treatment group. Clinical laboratory test data will be presented in listings.

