10.3 Clinical Laboratory Data

Summary statistics for the clinical laboratory parameters at baseline, post-dose time points, and mean changes from baseline will be presented. The incidence of potentially clinically significant laboratory test abnormalities will be summarized for each test. Investigator assessment of clinical significance will be listed for abnormal assessments.

Quabodepistat (OPC-167832)

Study 323-201-00007

Criteria for the potentially clinically relevant laboratory test abnormalities are provided in [Appendix 2](#).

In addition, the DAIDS Adverse Event Grading Tables will be used for identifying laboratory values of potential clinical relevance ([Appendix 1](#)).

According to FDA Guidance, laboratory measurements that signal the potential for drug-induced liver injury (DILI) will be reported. An incidence table and a listing will be provided for subjects who meet the criteria for potential serious hepatotoxicity will be provided (see [Section 10.8](#)).

Scheduled assessments will be summarized in tables. Unscheduled assessments will only appear in listings and in presentations for potentially clinically laboratory test abnormalities. If a test is identified as a repeat test, the repeat test value will replace the original value.

Baseline values are Day –1 values, or, if Day –1 values are not available, then baseline values will be the values collected during the screening period.

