10.4 Vital Sign Data

Vital signs are measured at screening, on Day –1, pre-dose on Day 1. Baseline values will be predose values taken prior to first IMP treatment on Day 1. If multiple pre-dose Day 1 values are recorded, the chronologically last recorded value prior to first IMP treatment on Day 1 will be taken to be the baseline value. If there are no pre-dose Day 1 values, then baseline values will be taken to be the last value recorded on Day –1; if Day –1 values are missing, then the last screening value will be taken to be the baseline value.

Descriptive statistics will be provided for change from baseline in vital signs parameters. Incidence of treatment-emergent potentially clinically significant vital sign results will also be summarized. Listings of potentially clinically significant abnormalities will also be provided. If vital sign assessments are repeated for the same visit, the last repeat values will be used for production of mean change from baseline. This is accomplished by sorting patient data by visit date and visit time (if applicable) within the same visit identification. Criteria for Identifying Vital Signs of Potential Clinical Relevance are provided in Appendices 2 and 3.

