10.8 Potential Serious Hepatotoxicity

According to FDA Guidance, laboratory measurements that signal the potential for drug-induced liver injury (DILI) will be reported. An incidence table and a listing will be provided for subjects who meet one or combinations of following criteria:

- 1) ALT or AST $\geq 3 \times$ upper limit of normal (ULN) (or baseline value for subjects with abnormal baseline)
- 2) increase in bilirubin $\geq 2 \times$ ULN (or baseline value for subjects with abnormal baseline)

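### SAP 10.3 lets a repeat laboratory value replace the original without limit, so the abnormality and liver tables can miss subjects whose repeat was within limits

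*SAP*

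**What the plan says.** SAP 10.3 (Clinical Laboratory Data) plans an abnormality table: "The incidence of potentially clinically significant laboratory test abnormalities will be summarized for each test". It also announces the potential-hepatotoxicity output, which SAP 10.8 specifies: "An incidence table and a listing will be provided for subjects who meet one or combinations of following criteria". Those criteria are ALT or AST at or above 3 × ULN and bilirubin at or above 2 × ULN, with the baseline value as the reference for subjects whose baseline was abnormal.

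Two adjacent sentences in SAP 10.3 decide which values are used. The first covers unscheduled samples: "Unscheduled assessments will only appear in listings and in presentations for potentially clinically laboratory test abnormalities". The second covers repeats: "If a test is identified as a repeat test, the repeat test value will replace the original value". Neither SAP 10.3 nor SAP 10.8 says that the abnormality or liver tables use all values or the worst value.

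For vital signs, SAP 10.4 words its rule more narrowly. Where an assessment is repeated at the same visit, "the last repeat values will be used for production of mean change from baseline".

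Protocol 8.6.1 gives the reason for repeating a test: "The investigator may repeat the laboratory test or request additional tests to verify the results of the original laboratory tests". Protocol 9.4.3.2 adds that "Clinical laboratory test data will be presented in listings". It does not say whether a replaced original stays in the listing.

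**The concern.** A repeat ordered to verify a result is ordered because of that result. Abnormal values are therefore the likely ones to be repeated, and a rule that keeps only the repeat discards originals selectively. That is tolerable for a mean by visit. It is not tolerable for a table meant to count subjects who ever crossed a threshold.

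Safety is the only secondary objective (Protocol Table 3-1), and the laboratory tables are its systematic record. Few scheduled samples fall after the interacting drug starts: Days 15, 16 and 26 in Part 1 (Table 1.3-1), and Days 11, 14, 25 and 32 in Part 2 (Table 1.3-2 footnotes). A subject with a transient ALT or AST rise or a low blood count may have only one qualifying value. If that value is replaced, the table shows nothing for that subject.

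**Working it through.** The plan gives no figure for this rule, so there is nothing to reproduce. The check is a reading of the text, followed by an illustration of scale.

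**Reading the rules side by side**

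| Rule | Same visit only? | Limited to certain outputs? |
|---|---|---|
| Vital signs, SAP 10.4 | Yes | Yes: mean change from baseline |
| Laboratory unscheduled values, SAP 10.3 | Not applicable | Yes: listings and abnormality presentations |
| Laboratory repeats, SAP 10.3 | Not stated | No limit stated |

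The narrower wording in 10.4 shows that the SAP can limit a repeat rule when it means to. The unscheduled rule shows that the abnormality outputs are meant to be inclusive. Under the two laboratory rules, a retest recorded as unscheduled adds to the original, while one recorded as a repeat removes it. The SAP does not define a repeat, so the count can depend on a label.

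**What happens to one subject whose original value meets a criterion**

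1. No repeat, or the retest is recorded as unscheduled: the subject is counted.
2. Recorded as a repeat, and the repeat still qualifies: the subject is counted, but the original magnitude (and possibly a higher DAIDS grade) is lost.
3. Recorded as a repeat, the repeat is within limits, and another value qualifies: the subject is still counted.
4. Recorded as a repeat, the repeat is within limits, and no other value qualifies: the subject is not counted.

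Only case 4 changes a by-subject incidence.

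**Scale**

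With 12 subjects per part (SAP 3), one subject is 1/12 = 8.3%. A single case 4 moves a reported incidence from 1/12 (8.3%) to 0/12.

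To illustrate further, let p be the chance that a subject has a qualifying original value, and q the chance that such a subject falls into case 4. Both are assumptions; the documents give neither. Treating subjects as independent,

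P(table shows at least one subject) = 1 − [1 − p(1 − q)]^12.

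| q | p = 1/12 | p = 2/12 |
|---|---|---|
| 0 (all values count) | 64.8% | 88.8% |
| 0.25 | 53.9% | 79.9% |
| 0.50 | 40.0% | 64.8% |
| 0.75 | 22.3% | 40.0% |
| 1 | 0% | 0% |

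Worked example, p = 1/12 and q = 0.5: p(1 − q) = 1/24, and 1 − (23/24)^12 = 40.0%. With q = 0: 1 − (11/12)^12 = 64.8%.

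**The case against.** The strongest reply is that the SAP never says the replacement rule feeds the abnormality and liver tables. It applies only to a test identified as a repeat, a term left undefined. A confirmatory draw entered as unscheduled would be counted beside the original. This is fair, and it means that loss of cases is a consequence of the wording, not something the documents demonstrate. It does not rescue the text: the sentence is unqualified, it sits in the section that sets up those tables, and nothing exempts them.

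The second reply is that other routes catch the events. Clinically significant post-screening laboratory abnormalities become adverse events (Protocol 8.5.1, 8.6.1), and laboratory data are listed. A reader might conclude from the replacement rule that abnormal results vanish from reporting altogether; these routes show that they need not. They are incomplete, however. Protocol 8.6.6 requires the immediately reportable event form only when bilirubin is also at or above 2 × ULN, whereas SAP 10.8 counts subjects meeting either criterion alone. An isolated ALT or AST elevation becomes an adverse event only if it is judged clinically significant, leads to discontinuation or is serious, and a normal repeat makes the first less likely.

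A reader might also infer that the bias always favours safety. It does not. A repeat can be worse than the original. The rule can also reach baseline samples: replacing an abnormal baseline with a normal repeat removes the baseline-referenced allowance in SAP 10.8, which lowers the threshold and can flag more subjects.

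Finally, a reader might equate the share of abnormal values that fail to reproduce with the share of cases deleted. The documents do not support that. Repeats are optional, they must be recorded as repeats, and the subject must have no other qualifying value.

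**Conclusion.** The point holds in a limited form. Followed as written, SAP 10.3 leaves out of the abnormality, DAIDS-grade and liver tables any subject whose only qualifying value was replaced by a repeat within limits. Where the repeat still qualifies, the subject remains and only the size of the original abnormality is lost. The direction is predominantly toward under-reporting, on the assumption that verification repeats are ordered mainly for abnormal results.

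Each affected subject is worth 8.3 percentage points in a part of 12. How many would be affected cannot be derived from the documents, and the percentages for assumed p and q are illustrations only.

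This should be fixed, but it is not critical to the trial's main conclusion. The laboratory tables are descriptive, and the primary pharmacokinetic comparison does not use them. The documents also give no basis for requiring the original value in by-visit summaries: SAP 10.4 uses the last repeat for mean change, and doing the opposite for laboratory data would introduce a new inconsistency.

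**What to change.** Amend SAP 10.3, with a cross-reference in 10.8, as follows:

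- Limit replacement by a repeat to by-visit descriptive and change-from-baseline summaries, in line with SAP 10.4.
- In the abnormality, DAIDS-grade and hepatotoxicity tables, count all valid post-dose values (original, repeat and unscheduled), taking the worst case per subject. Exclude an original only when the laboratory documents the specimen as invalid.
- Show both original and repeat values in the listings.
- Define what identifies a test as a repeat as opposed to an unscheduled test.

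The cost is a few lines of SAP text and a little extra programming, with no new data or procedures. The downside is that some unconfirmed transient values will be counted; listing the repeat beside the original lets the reader judge them.

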2.3 Known and Potential Risks and Benefits

Subjects will receive no health benefit from participation in this trial.

Single oral doses up to 480 mg OPC-167832 were well tolerated during Trial 323-201-00001; there were no serious or severe AEs and no subjects were discontinued from the trial due to a treatment-emergent AE. One subject did decide to withdraw consent after occurrence of the nonserious and mild AEs of arthralgia, pain in extremity, and ecchymosis.¹ There was a slight negative correlation observed between changes in QT interval corrected for heart rate using Fridericia's formula (QTcF) from baseline and placebo, and OPC-167832 plasma concentrations. There is currently 1 ongoing trial (Trial 323-201-00003) that is evaluating the safety of OPC-167832 in adult subjects with uncomplicated DS pulmonary TB. There was 1 SAE of haemoptysis (3 mg group in Stage 1), which led to discontinuation of investigational medicinal product (IMP). This SAE was not considered to be causally related to the IMP but as a complication of the underlying pulmonary TB. There was 1 SAE of anal abscess (30 mg OPC-167832 and 400 mg bedaquiline group in Stage 2), which led to discontinuation of IMP and was considered unrelated to the IMP.¹

In 1-, 4-, and 26-week toxicity studies in rats, no drug-related deaths occurred in either males or females at any dose tested. Suppressed body weight gain and/or decreased food consumption were observed and increases in total cholesterol and phospholipids and decreases in creatinine were observed at 1 week. These changes showed reversibility or a tendency for reversibility.

In 1-, 4-, 13- and 39-week toxicity studies in dogs, no treatment related deaths occurred in either males or females at any dose tested. Increases in creatinine kinase, alanine aminotransferase (ALT), aspartate aminotransferase (AST), lactate dehydrogenase, and potassium were observed in the 4-week toxicity study at the highest dose (2000 mg/kg/day). Increases in total cholesterol and phospholipids were also observed in the 4- and 13-week toxicity studies at doses of 100 mg/kg/day and higher. In the 4-week toxicity study, slight prolongation of QT interval and QTc was observed at Week 4 in both sexes at 2000 mg/kg/day. However, no prolongation of QT interval and QTc was noted in the 13-week toxicity study in either sex at up to 100 mg/kg.

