6.1 Trial Intervention(s) Administered

Trial interventions are all pre-specified, investigational and noninvestigational medicinal products intended to be administered to the subjects during the conduct of the trial.

OPC-167832, itraconazole, and carbamazepine will be administered orally to subjects as per the dosing schedule in Table 6.1-1. OPC-167832 CCI will be provided as 30-mg tablets, itraconazole will be administered as a 10-mg/mL oral solution, carbamazepine will be administered as the least number of tablets based on commercially available extended-release tablets (ie, 100-mg tablet, 200-mg tablet). Lower dose strengths of carbamazepine can be combined, ie, a 100-mg tablet and a 200-mg tablet

should be combined to dose at 300 mg. All doses will be administered with approximately 240 mL of room temperature, still water. When itraconazole is administered, some of the 240 mL of water should be used to rinse the dosing container. All doses of OPC-167832 (administered on Days 1 and 15 in Part 1 and Days 1 and 25 in Part 2) will be administered following an overnight fast of at least 10 hours.

For Part 1, OPC-167832 and itraconazole will be administered in the morning at the same time each day. The BID dose of itraconazole on Day 8 will be administered every 12 hours (q12h). On days of serial PK sampling days (Days 1 and 15), subjects will be required to continue to fast from food for at least 4 hours following dosing of OPC-167832 and water will be restricted for 1 hour before to 2 hours after dosing of OPC-167832. Water is permitted ad libitum on all other days.

For Part 2, OPC-167832 and carbamazepine will be administered in the mornings at the same time each day and BID doses of carbamazepine will be administered q12h and at same time each evening. On days of serial PK sampling days (Days 1 and 25), subjects will be required to continue to fast from food for at least 4 hours following dosing of OPC-167832 and water will be restricted for 1 hour before to 2 hours after dosing of OPC-167832. Water is permitted ad libitum on all other days.

For information regarding the dosage regimen and treatment period(s), including any follow-up period(s) for each treatment group/part of the trial, see [Section 4.1](#).

Table 6.1-1 Dosing Schedule		
Study Day	Time	Dose
PART 1		
1	morning	30 mg OPC-167832
8	morning	200 mg itraconazole
	evening	200 mg itraconazole
9 through 14	morning	Once-daily 200 mg itraconazole

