8.8 Protocol Deviations

Major protocol deviations, as recorded in the eCRF, will be listed.

9 Efficacy Analyses

Not applicable

10 Safety Analyses

The safety analysis will be conducted on the safety analysis set for each part separately. Safety variables to be analyzed include AEs, clinical laboratory assessments, vital signs,

Quabodepistat (OPC-167832)

Study 323-201-00007

12-lead ECGs, physical examinations, and the Columbia-Suicide Severity Rating Scale ([C-SSRS] Part 2 only). Descriptive statistics will be provided for the safety variables. Baseline measurements of safety variables are defined as the last measurement prior to the first dosing of IMP (also see [Section 6.7](#)).

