11.3 Technical Details of Pharmacokinetic Statistical Analyses

Not applicable.

12 Pharmacodynamic Analyses

Not applicable.

14 Interim Analysis

None.

Quabodepistat (OPC-167832)

Study 323-201-00007

15 Changes in Planned Analysis

None.

Quabodepistat (OPC-167832)

Study 323-201-00007

16 References

- 1 United States Department of Health and Human Services, Division of AIDS, National Institute of Allergy and Infectious Diseases, National Institutes of Health. Division of AIDS (DAIDS) Table for Grading the Severity of Adult and Pediatric Adverse Events; 2017 (version 2.1).

17 Document History

Dates/Author	Description of Updates	Version	Document Updates
26 September 2022/ CCI [REDACTED]	draft	1.0	Not Applicable
25 January 2023/ CCI [REDACTED]	draft: 
 1) updated Appendix 1. Criteria now includes only parameters relevant to the study. 2) updated Appendix 2. The entire DAIDS table has been included as Appendix 2. 3) included QTxx > 480 msec (males and females) criterion for QT, QTcF and QTcB in Appendix 5. 4) clarified collection of relatedness of adverse events to IMP and its components. 5) Other minor updates to text for greater clarity and readability. 	1.1	Applied.
13 March 2023/ CCI [REDACTED]	Final version: 1) clarifications to text	1.0	

OPC-167832

Study 323-201-00007

Appendix 1 Definition of Grades in Serum Chemistry, Hematology and Urinalysis Lab Test Results in the Division of AIDS (DAIDS) Table for Grading the Severity of Adult and Pediatric Adverse Events

The table below contains reference to the criteria provided in the DAIDS table. The DAIDS table v2.1 is attached as [Appendix 2](#) to this SAP.

Protocol Assessment	DAIDS Grading Table Row(s)	Page in DAIDS grading tables
Hematology		
Hemoglobin	Hemoglobin, Low (≥ 13 years of age (female only)	29
	Hemoglobin, Low (≥ 13 years of age (male only)	29
Hematocrit	-	-
Mean corpuscular hemoglobin concentration	-	-
Mean corpuscular volume	-	-
RBC count	-	-
WBC count (absolute and differential)	WBC, Decreased	30
Platelets	Platelets, Decreased	30
Serum Chemistry		
Alkaline phosphatase	Alkaline phosphatase, High	25
Alanine aminotransferase	ALT or SGPT, High	25
Aspartate aminotransferase	AST or SGOT, High	25
Bilirubin, total (with reflex if elevated)	Total bilirubin, High	25
Blood urea nitrogen	-	-
Calcium	Calcium, High	26
	Calcium, Low	27
	Calcium (ionized), Low	28
Cholesterol	Cholesterol, Fasting, High	27
Creatinine	Creatinine, High	26

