	Creatinine Clearance or eGFR, Low	26
Gamma glutamyl transferase	-	-
Glucose	Glucose, Fasting, High	26
	Glucose, Nonfasting, High	26
	Glucose, Low	27
Lactate dehydrogenase	Lactate, High	27
Magnesium	Magnesium, Low	27
Potassium	Potassium, Low	27

OPC-167832

Study 323-201-00007

	Potassium, High	27
Protein, total	-	-
Sodium	Sodium, High	28
	Sodium, Low	28
Triglycerides	Triglycerides, Fasting	27
Urinalysis		
Glucose or glycosuria	Glycosuria	31
Blood or hematuria	Hematuria	31
Protein or proteinuria	Proteinuria	31
Drug screen	-	-
Additional Tests		
Urine or serum pregnancy test	-	-
Follicle-stimulating hormone for post-menopausals	-	-
Serology (hepatitis B surface antigen, hepatitis C antibodies, human immunodeficiency virus)	-	-

OPC-167832

Study 323-201-00007

Appendix 2**Division of AIDS (DAIDS) Table for Grading the Severity of Adult and Pediatric Adverse Events (Corrected Version 2.1, July 2017)**

Glossary and Acronyms	
Acronym	Definition
AE	Adverse event; Any unfavorable and unintended sign (including an abnormal laboratory finding), symptom, or disease temporally associated with the use of a medical treatment or procedure regardless of whether it is considered related to the medical treatment or procedure.
ALT (SGPT)	Alanine aminotransferase (serum glutamic pyruvic transaminase)
ANC	Absolute neutrophil count
AST (SGOT)	Aspartate aminotransferase (serum glutamic-oxaloacetic transaminase)
AV	Atrioventricular
Basic Self-care Functions	Adult : Activities such as bathing, dressing, toileting, transfer or movement, continence, and feeding. Young Children : Activities that are age and culturally appropriate, such as feeding one's self with culturally appropriate eating implements.
BMI z-score	Body mass index z- score; A body reference norm. Specifically, the number of standard deviations a participant's BMI differs from the average BMI for their age, sex, and ethnicity.
BMD t-score	Bone mineral density t-score; The number of standard deviations above or below the mean bone mineral density of a healthy 30 year old adult of the same sex and ethnicity as the participant.
BMD z-score	Bone mineral density z-score; The number of standard deviations a participant's BMD differs from the average BMD for their age, sex, and ethnicity.
BPAP	Bilevel positive airway pressure; A mode used during noninvasive positive pressure ventilation.

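### Lipids are graded on DAIDS fasting limits, and glucose on either of two rows with no selection rule, although most laboratory draws, including baseline, require no fast and no record of fasting status

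*SAP*

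**What the plan says.** **Grading.** SAP 10.3 uses the DAIDS tables to identify laboratory values of potential clinical relevance. SAP Appendix 1 maps cholesterol to "Cholesterol, Fasting, High" and triglycerides to "Triglycerides, Fasting", with no nonfasting row for either. For high glucose it lists the fasting row and also "Glucose, Nonfasting, High". It gives no rule for assigning a sample to a row.

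**Baseline.** Protocol 9.4.3.2 states: "Baseline is defined as the last nonmissing value obtained at a scheduled visit on or before Day -1". SAP 10.3 agrees: "Baseline values are Day –1 values, or, if Day –1 values are not available", the screening value is used. Both plan summaries of change from baseline and of the incidence of abnormalities.

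**Fasting.** Protocol 6.1 says that all OPC-167832 doses "will be administered following an overnight fast of at least 10 hours", and extends the fast for at least 4 hours after the dose. This covers Days 1 and 15 in Part 1 and Days 1 and 25 in Part 2. Protocol 8.5.1, both schedules of assessments and SAP 10.3 set no fasting condition for laboratory draws and do not mention recording fasting status.

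**The concern.** A fasting limit is meaningful only for a fasted sample, and a change from baseline only if both samples were taken in a comparable state. As written, the plan guarantees neither for triglycerides, cholesterol and glucose. A grade may reflect a meal, and a mean change at a fasted visit may compare that visit with a check-in sample drawn after food.

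In Part 2 the one draw certain to be fasted (Day 25, before OPC-167832 but on carbamazepine) is compared with a baseline of unspecified fasting state. If status is not recorded at the draw, the analysis cannot later separate a food effect from a drug effect.

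Lipids have some relevance for this compound. Of the dog studies, protocol 2.3 reports: "Increases in total cholesterol and phospholipids were also observed in the 4- and 13-week toxicity studies". It reports similar changes in rats.

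**Working it through.** The plan gives no figure of its own on this point. The check is a count of draws and a comparison of grade limits.

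**1. Scheduled laboratory draws against required fasts** (protocol Tables 1.3-1 and 1.3-2 with footnotes; protocol 6.1)

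| Part | Laboratory draw days | Required fast that day? | Draw stated as predose? |
|---|---|---|---|
| 1 | Screening, -1 (baseline), 2, 16, 26 | No | No |
| 1 | 1, 15 | Yes | No |
| 2 | Screening, -1 (baseline), 32 | No | No |
| 2 | 8, 11, 14 | No | Yes |
| 2 | 25 | Yes | Yes |

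- Part 1: 2 of 7 draw days fall on a day with a required fast.
- Part 2: 1 of 7. Day 1 is a fasting day in Part 2, but no laboratory draw is scheduled on it.
- Together: 2 + 1 = 3 of 7 + 7 = 14.
- Baseline draws among the 3: none.

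The 3 is an upper limit. The laboratory row in Table 1.3-1 carries no time of day, so a Part 1 Day 1 or Day 15 sample could be drawn after the 4-hour postdose fast has ended. Only Part 2 Day 25 is both on a fasting day and labelled predose.

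**2. Glucose: does the row matter?** (limits in mg/dL, SAP Appendix 2, Chemistries)

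| Glucose | Fasting row | Nonfasting row |
|---|---|---|
| 110-115 | Grade 1 | ungraded |
| 116-125 | Grade 1 | Grade 1 |
| >125 to 160 | Grade 2 | Grade 1 |
| >160 to 250 | Grade 2 | Grade 2 |

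The rows disagree in two bands, 110-115 and >125 to 160. Two programmers could follow this SAP and produce different counts from the same data. This needs no outside assumption.

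**3. Triglycerides: illustration of the change from baseline.** SAP Appendix 2 starts Grade 1 at 150 mg/dL fasting. *Assumption, not in the documents: a meal raises triglycerides by 20 to 60 mg/dL.* Take an invented subject with a fasting value of 130 before treatment and a fasting value of 155 on treatment.

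- True change: 155 - 130 = +25.
- Baseline if fed: 130 + 20 = 150 to 130 + 60 = 190, which is Grade 1, although the fasting value of 130 is ungraded.
- Reported change: 155 - 150 = +5 to 155 - 190 = -35.

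This shows the direction and possible size for one subject. It is not an estimate of what the trial will show.

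**The case against.** The strongest reply is that silence about fasting does not show that any sample is fed. The protocol defers operational detail to manuals that are not available here and that could require a fast. The Part 2 draws on Days 8, 11 and 14 precede a morning dose and may well precede breakfast. The DAIDS rows are labelled by fasting state, so a careful programmer would apply each to matching samples. The tables affected are descriptive, with 12 subjects per part, and the investigator's view of clinical significance is listed. All of this stands, and it limits the point to what may happen. It does not close the gap: matching rows to samples requires a fasting status that neither document collects, and cholesterol and triglycerides have no alternative row.

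A reader might infer more than the documents support:

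- *That the samples do mix fed and fasted states, or that grades at baseline, Day 26 or Day 32 are false.* No text says that any sample is fed.
- *That the Part 1 Day 15 laboratory sample is a fasted predose sample.* The schedule does not time it.
- *That a true rise would be lost from the grade counts.* The incidence summary in SAP 10.3 has no treatment-emergent condition, so the 155 mg/dL value above would still count as Grade 1. Only the change from baseline is distorted.
- *That the SAP contradicts itself on baseline and Part 1 should use Day 1.* SAP 10 says baseline is "defined as the last measurement prior to the first dosing of IMP", but it refers to SAP 6.7, which sends laboratory data to 10.3. The specific rule governs and agrees with protocol 9.4.3.2.
- *That the animal findings make triglycerides or glucose a known signal.* They concern total cholesterol and phospholipids in repeated-dose studies. Phospholipids are not in the panel, and this trial gives two single 30-mg doses.

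**Conclusion.** The concern holds in a limited form and should be corrected. Fasting limits are assigned to samples that need not be fasted, there is no rule for choosing the glucose row, and fasting status is not recorded under either document. At most 3 of 14 draw days are tied to a required fast, none of them a baseline, and one is certain to be fasted. Grades and mean changes for cholesterol, triglycerides and glucose may therefore mix fed and fasted samples.

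The glucose ambiguity follows from the SAP's own limits. The size of any triglyceride distortion rests on the assumed meal effect. The conclusion also assumes that no manual outside these documents sets a fast or captures fasting status; if one does, the remaining need is to state this in the SAP with the row rule. Only descriptive safety summaries for three analytes are affected. The primary PK analysis does not depend on them.

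**What to change.** **Protocol 8.5.1 and the schedules of assessments.** Draw the scheduled post-screening chemistry samples after an overnight fast: Day -1 in both parts; Days 1, 2, 15, 16 and 26 in Part 1; Days 8, 11, 14, 25 and 32 in Part 2. State that the Part 1 Day 1 and Day 15 laboratory samples are predose. Record fasting status at every draw, including screening, because a screening value can serve as baseline.

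**Baseline.** Keep Day -1, in line with protocol 9.4.3.2. Once that sample is fasted, moving baseline is unnecessary.

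**SAP 10.3 and Appendix 1.** Apply the fasting lipid and glucose rows only to fasted samples and the nonfasting row to other glucose values. Leave nonfasted lipids ungraded. Flag changes from baseline where fasting status differs between the two samples or is unknown.

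**Cost.** One eCRF field, a line in each schedule and some SAP text, with no added samples. Of the 12 post-screening draw days listed, 3 already fall under a required fast, so 9 fasts are new: 4 in Part 1 and 5 in Part 2. One in each part is before check-in; the rest (3 and 4) are before in-clinic draws in resident subjects. If sampling can no longer be changed, the SAP rules still apply, with fasting status shown as unknown where it was not captured.
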